9. RESEARCH METHODS

To achieve the study objectives, retrospective medical record data of adult patients diagnosed with locoregional RCC who received a nephrectomy at Duke will be compiled by Duke researchers and analyzed by RTI Health Solutions (RTI-HS) analysts. RTI-HS will develop a customized data-collection form (DCF) to capture detailed information on patient demographics, clinical characteristics, health outcomes, treatments, and postoperative referrals from the medical records of eligible patients. Patients will be selected based on specific inclusion and exclusion criteria described in [Sections 9.2.1](#) and [9.2.2](#). All necessary study materials will be submitted to Duke's institutional review board (IRB) for review and RTI International's¹ IRB for study classification.

Following receipt of each IRB's classification or approval of the study (where required), Duke researchers will proceed with implementation of the pilot study (pilot phase). The pilot phase will consist of a pilot study to assess whether an adequate sample of the patient population of interest is available, evaluate the quality and completeness of available data, and quantify the duration of follow-up care available in Duke's electronic medical record (EMR) system. Using lessons learned from the pilot study, part 2 (the full study) will consist of abstracting data for a large sample of patients, analyzing the data, and preparing a study report and other materials for disseminating the study findings (ie, conference abstract, poster, and manuscript). Based on the temporal trends observed in part 2, the data abstraction will be expanded to include part 3 (the expanded study), which will consist of abstracting data on the additional patients who underwent nephrectomy through 2019 and expanded follow-up data collection (ie, referral patterns, treatment patterns, and outcomes) for previously identified patients at high risk of recurrence, to include follow-up dates through the most recent available medical record entry prior to the abstraction date.

[figure not shown]
¹ RTI Health Solutions is a business unit of the not-for-profit research organization RTI International.

9.1. Study Design

This study is a retrospective, observational medical record review of patients diagnosed with locoregional RCC who received a nephrectomy at Duke between 01 April 2014 and 31 December 2019. The date of the nephrectomy will be considered the *index date*.

Background clinical characteristics such as date of initial and locoregional RCC diagnoses will be identified during the period prior to the index date. Recurrence risk status will be assigned at the index date, using information available in the record at or around the index date. During the follow-up period (ie, the period between the index date and the last entry in the medical record, death, or disease recurrence), outcomes including treatment, referrals, and disease recurrence will be assessed for patients who were determined to have been at high risk of recurrence following their nephrectomy, where data are available. Figure 1 provides a visual schematic of relevant observation periods.

Figure 1. Patient Observation Periods

RCC = renal cell carcinoma.

9.1.1. Pilot Phase

To enable assessment of appropriate inclusion criteria and data availability, researchers will conduct an initial pilot study. Duke researchers have compiled a preliminary list of patients diagnosed with RCC who underwent nephrectomy between 01 November 2012, and 31 October 2018, using DEDUCE, Duke's EPIC query tool. A total of 1,069 patients were identified, of which approximately 75% (n = 801) are expected to have been diagnosed with locoregional disease. A total of 883 patients were identified between 01 November 2013, and 31 October 2018 (approximately 662 anticipated to have locoregional disease). At this time, the researchers anticipate that a total sample of approximately 500 patients diagnosed with locoregional RCC who underwent nephrectomy will be required to obtain a sample of 75 to 100 patients considered to have been at high risk for disease recurrence after surgery.

Based on these preliminary counts, it is likely that inclusion of nephrectomies occurring between 01 November 2013, and 31 October 2018, will generate a sufficient sample. Duke researchers will determine preliminary annual aggregated counts, which RTI-HS will use to estimate the anticipated sample size of patients at high risk of recurrence, based on a published algorithm (eg, UCLA Integrated Staging System [UISS] risk status or stage, size,

grade, and necrosis [SSIGN] score) and proportions identified in published literature. Assessing potential sample size during the pilot study will allow researchers to determine whether the proposed sampling strategy (ie, selecting nephrectomy between 01 November 2013, and 31 October 2018) is adequate to obtain the desired sample size. If it is not, nephrectomies occurring from 01 November 2012, may be considered.

After the updated preliminary count is established and the study is approved by Duke's IRB, Duke researchers will evaluate the quality and completeness of available data by abstracting data for at least 20 eligible patients by reviewing patient medical records from a random sample of 50 patients identified by the DEDUCE query tool. This process will determine the proportion of eligible patients in the broader patient list identified by DEDUCE, and whether adequate information required to meet the study objectives are regularly available in the medical record. Results of the pilot study will be used to inform the final sample size expectation and refine study objectives, as needed. Note that a full assessment of data availability is dependent on abstraction of one or more patients that are classified as being at high risk of recurrence. If the first 20 eligible patients abstracted do not include a patient that is classified as high risk, additional patients will be included in batches of five until data for at least one patient at high risk of recurrence have been abstracted.

9.1.2. Part 2: Full Study

Results from the pilot phase feasibility assessment validated the sample size assumptions, with 83% of nephrectomies identified in the DEDUCE query confirmed eligible for the study and 15% of eligible nephrectomies classified as high risk. This indicates that the minimum sample of 500 patients, with 75-100 high risk, will likely be exceeded. Nephrectomies between 01 April 2014 and 31 March 2019 will be included to ensure the most up-to-date patient sample.

Part 2 will consist of abstracting data for the full sample of eligible patients, analyzing the data, and reporting the results. Duke researchers will abstract data on the remaining sample of eligible patients. Baseline demographic and clinical characteristics will be abstracted for the anticipated sample of 500 patients. Of patients who are determined to be at high risk of recurrence following nephrectomy (anticipated sample of 75-100 patients), additional data on treatment characteristics, outcomes, and referrals will be abstracted.

Once the data are fully abstracted, anonymized patient-level data will be transferred to RTI-HS for analysis. All programming will be conducted using SAS statistical software (version 9.4 or higher). The analysis will be descriptive, with exploratory models to examine possible factors associated with disease recurrence and disease-free interval, if the sample size is sufficient.

9.1.3. Part 3: Expanded Data Collection

Results from the part 2 study indicated that referral and treatment patterns show an increasing trend from 2018 into 2019. To further capture this trend, an additional sample of all patients with nephrectomies occurring through 31 December 2019 will be abstracted. The additional sample size during this period is estimated to be approximately 115-150 patients, for a full

combined sample of up to 650 patients in total. In addition, expanded follow-up data (ie, referral patterns, treatment patterns, and outcomes) will be collected for previously identified patients at high risk of recurrence, to include follow-up dates through the most recent available medical record entry prior to the abstraction date.

9.2. Setting

Data will be abstracted from the Duke EMR system. Patients whose data will be included in the study will have met the criteria described in [Sections 9.2.1](#) and 9.2.2. Refer to [Figure 1](#) for a depiction of the follow-up period. No minimum follow-up time will be required. Outcomes among patients who are determined to be at high risk of recurrence will be observed over each patient's follow-up period—from the date of nephrectomy to death, disease recurrence, or the last date in their medical record (whichever occurs first).

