Study design: Non-interventional, retrospective medical record review of patients diagnosed with locoregional RCC who received a nephrectomy in Duke University's health system (Duke). Using a published algorithm (eg, the UCLA Integrated Staging System [UICC] or the stage, size, grade, and necrosis [SSIGN] score) or adaptation of a published algorithm, patients at high risk of recurrence following surgery will be followed until the end of their patient record, death, or disease recurrence to examine referral patterns, receipt of systemic therapy, disease recurrence, and death. The study will consist of a pilot phase to test the data abstraction tool and determine feasibility of assessing the study objectives with available data and a full abstraction phase to compile the necessary data, conduct the analyses, and generate the documents for dissemination of the study results.

Population: Patients aged 18 years or older who were diagnosed with locoregional RCC and underwent nephrectomy at Duke between 01 April 2014 and 31 December 2019. The final date range for patient inclusion was determined after the part 2 data collection was complete.

Variables: Background (eg, age at nephrectomy, sex) and baseline clinical characteristics (eg, performance status, TNM [tumor, node, metastasis] stage, histology, tumor grade, categorical risk of recurrence following nephrectomy by commonly used clinical nomograms); postnephrectomy treatment and referrals; and disease recurrence events and survival will be assessed, where available.

Data sources: Duke researchers will abstract the necessary information from the electronic medical records of eligible patients and enter deidentified information into the study database. This study is retrospective; therefore, the collection of data will in no way influence prescribing patterns or treatment decisions.

Study size: Data will be abstracted from a target of 20 eligible patients during the pilot phase. During full abstraction, data for approximately 650 patients will be targeted for abstraction.

Data analysis: Descriptive summary of baseline characteristics by UISS risk categories among patients with locoregional RCC. Among patients at high risk of recurrence, descriptive summary of postnephrectomy follow-up care. Time-to-event outcomes (eg, disease-free interval) will be described using the Kaplan-Meier method, if feasible.

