9.3.6. Outcomes (high-risk subgroup only)

Health outcomes will be collected only for patients at high risk of recurrence, when available.

- Date of last follow-up encounter in the medical record;
- Date of death;
- Date of disease recurrence and method of confirmation;
- Type of disease recurrence (eg, locoregional versus distant, if applicable);
- Reasons for treatment discontinuation.

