9.4. Data Sources

Data will be abstracted from medical records of patients receiving care within the Duke University Health System. This study is retrospective; therefore, the collection of data will in no way influence prescribing patterns or treatment decisions.

Medical record abstractions provide a unique opportunity to collect and analyze real-world data outside the highly controlled setting of clinical trials. Generally, medical record abstraction enables collection of detailed information on patient demographic and clinical characteristics, treatment patterns, health outcomes, and health care resource utilization (HCRU) that may otherwise be unavailable in a standardized manner. The use of medical record abstraction allows for the development of a highly customized DCF that meets the specific needs of this study.

Following ethics approval, the DCF will be programmed into an Excel-based data-collection instrument. The use of an Excel-based tool not only enables streamlined abstraction but also real-time consistency checks to improve the accuracy of the recorded data. Upon finalization of the DCF, physicians at Duke will proceed with data-collection activities. Physicians will screen their patients' records to identify eligible patients. Physicians will be responsible for selecting patient medical records that meet the inclusion and exclusion criteria described in [Section 9.2](#). After the physician identifies an eligible medical record, he or she will complete the DCF for the patient by retrospectively reviewing all available data in the medical record. The use of physicians to directly abstract patient medical record data eliminates interviewer or abstractor bias. Additionally, physicians are able to quickly and accurately interpret notes contained within a patient record, thereby providing additional information from a qualitative source. See [Section 9.9](#) for a detailed review of the strengths and limitations of this study type.

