9.7. Data Analysis

All variables described in [Section 9.3](#) will be summarized descriptively through the tabular display of mean values, 95% confidence intervals (CIs), medians, quartiles, and standard deviations of continuous variables of interest and frequency distributions for categorical variables. All open-ended text fields associated with the “other” answer option will be evaluated and described, as appropriate.

All study-eligible patients will be included in descriptive analyses of variables pertaining to patient characteristics, baseline clinical characteristics, and initial postoperative follow-up visits (see [Sections 9.3.1](#), [9.3.2](#), and [9.3.3](#) for details). Patients who are categorized as having a high risk of recurrence will be included in additional analyses described below. Risk classification will be assessed using published algorithms (eg, UISS and SSIGN score) or adaptation of a published algorithm. The primary risk classification system used to designate the high-risk subgroup for this study will be chosen based on completeness of data available in the patient medical records. Completeness will be assessed during the pilot study. If data are available to support more than one classification system, the UISS risk classification will be used. If some data are not available to support classification using a published algorithm, an adapted version of an algorithm will be explored.

Additional descriptive analyses performed within the high-risk subgroup will include referral patterns, treatment patterns, and health outcomes (see [Sections 9.3.4](#), [9.3.5](#), [9.3.6](#)). In addition to descriptive analyses, time-to-event measures (ie, time to recurrence, overall survival) will be assessed. To adjust time-to-event measures, a Kaplan-Meier method that accounts for right-censoring will be implemented (Klein and Moeschberger, 2005).⁷ To evaluate time to recurrence, the endpoint will be programmed with the date of recurrence or date of death, whichever occurs first, as an eligible event; if neither of these events occurred, the outcome will be right censored at the date of the last medical record follow-up. To evaluate overall survival, the endpoint will be programmed with the date of death as an eligible event or right censored at the date of the last medical record follow-up.

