Exploratory semiparametric Cox proportional hazards models will be used to evaluate factors associated with time to recurrence and overall survival. These outcomes will be defined as described previously. Separate models will be estimated for time to recurrence and overall survival. The models will take the following general form:

$$h(t) = h_0(t) \exp(\beta_1 \text{DEMOGRAPHIC}_i + \beta_2 \text{CLINICAL}_i), \text{ (Equation 2)}$$

Where the following apply:

- $h(t)$ will be the hazard function of recurrence and overall survival as a function of explanatory variables.

- $h_0(t)$ will be the baseline hazard of recurrence and overall survival.
- DEMOGRAPHIC will be a vector of patient demographic characteristics, including but not limited to the following:
 - Age;
 - Sex.
- CLINICAL will be a vector of underlying clinical characteristics, including but not limited to the following:
 - Tumor histology;
 - Type and duration of systemic treatment;
 - Referral status;
 - Subsequent procedures.

The independent variables included in the final Cox proportional hazard models will be selected through an iterative process. First, separate univariate models assessing the relationship between each potential independent variable (eg, tumor histology) and the time-to-event outcome (ie, recurrence and overall survival) will be fit (Klein and Moeschberger, 2005).⁷ The model with the lowest Akaike information criteria (AIC) will be selected for further evaluation. Next, each unselected variable will be added independently to the previously selected model to determine whether the addition of the specific variable results in a lower AIC. The model with the lowest AIC will be selected for further evaluation. This process will be repeated with each of the remaining unselected variables until the addition of unselected variables no longer lowers the AIC. The most parsimonious model will have the lowest AIC. Additionally, variables of clinical significance may be included in the model. The overall goodness-of-fit of the final model will be assessed using Cox-Snell residuals and the proportional hazards assumption for the final set of covariates (Klein and Moeschberger, 2005).⁷

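### The follow-up window in the Abstract, 9.1 and 9.2 closes at recurrence, but 9.7 runs overall survival to death or last record, and no readable text says which rule governs

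*Combined protocol and SAP*

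**What the plan says.** **Text that ends observation at recurrence.** Section 9.2 observes the outcomes of high-risk patients "from the date of nephrectomy to death, disease recurrence, or the last date in their medical record (whichever occurs first", and makes no exception for survival. Section 9.1 defines the follow-up period as running from the index date to "the last entry in the medical record, death, or disease recurrence", and lists treatment, referrals and recurrence as assessed within it. The Abstract has high-risk patients "followed until the end of their patient record, death, or disease recurrence", although death is among the outcomes to be examined.

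**Text that does not.** Section 9.7 has overall survival "programmed with the date of death as an eligible event or right censored at the date of the last medical record follow-up". It then adds Cox regression on the same definition: "Separate models will be estimated for time to recurrence and overall survival".

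**Text on data collection.** Section 9.3.6 lists date of death and "Date of last follow-up encounter in the medical record" for high-risk patients, when available, without tying either to recurrence status. Section 9.4 has the physician complete the DCF "by retrospectively reviewing all available data in the medical record". The introduction to Section 9 and Section 9.1.3 extend referral, treatment and outcome data to the latest record entry, but for previously identified high-risk patients.

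**The concern.** A patient who recurs at month 12 and dies at month 30 is a death at month 30 under 9.7. Under the 9.2 window, observation stops at month 12 and the death is never seen. If that window fed the overall survival analysis, patients would be censored at the moment their risk of death rises. Such censoring is informative. The Kaplan-Meier curve would lie too high, and the Cox model, fitted to the same truncated data, would carry the same bias.

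The analyst might not notice. Abstraction is done at the study site and analysis elsewhere (Section 9). Only day differences from the index date are transferred (Section 10), and no independent reviewer checks entries against the records (Section 9.9).

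The window also bears on description. Section 8 asks for postoperative referrals and for treatment after nephrectomy in high-risk patients, and limits neither to the time before recurrence. Section 9.1 assesses both inside a period that closes at recurrence.

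**Working it through.** **Step 1. Apply each rule to each endpoint.**

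| Item | Window (Abstract, 9.1, 9.2) | Section 9.7 or Section 8 | Compatible? |
|---|---|---|---|
| Time to recurrence | stops at first of recurrence, death, last record | event is recurrence or death, whichever is first; otherwise censored at last record | yes |
| Overall survival | same stop | event is death; otherwise censored at last record | no, for anyone who recurs |
| Referrals and treatment | same stop | Section 8 gives no stop at recurrence | unclear |

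**Step 2. Does other text settle it?** Sections 9.3.6 and 9.4 make ordinary overall survival feasible, but they describe fields and chart review, not an observation period. The extension in Sections 9 and 9.1.3 reaches the latest record entry, but it covers earlier high-risk patients, does not mention recurrence, and leaves the 9.2 wording in place. Section 9.3.5 calls the systemic therapy adjuvant where it lists dates, which narrows the treatment question somewhat. Section 9.3.4 sets no such limit on referrals.

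**Step 3. Patients concerned.** Section 9.5: 650 × 0.15 = 97.5 (98) and 650 × 0.20 = 130, so its 98-130 reproduces. If 20-40% of them recur (assumed), between 98 × 0.20 = 19.6 and 130 × 0.40 = 52 patients would leave observation at recurrence.

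**Step 4. Illustration of the bias if the window governs.** The plan gives no figure to reproduce. Assumed inputs, with constant hazards and no loss to follow-up:

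- r, recurrence by 5 years: 0.20-0.40. Section 7 gives up to 40% relapse for regional disease, with no time horizon.
- d, death without recurrence by 5 years: 0.05-0.15.
- s, 5-year survival after recurrence: 0.12-0.50. The 12% in Section 7 is for distant disease at diagnosis; no figure for relapse is given.

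Monthly hazards are hr = -ln(1-r)/60, hd = -ln(1-d)/60 and hp = -ln(s)/60. With a = hr + hd:

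- true OS(t) = exp(-a·t) + hr·[exp(-hp·t) - exp(-a·t)]/(a - hp)
- curve censored at recurrence = exp(-hd·t)

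Largest gap (r = 0.40, d = 0.05, s = 0.12): hr = 0.00851, hd = 0.00085, hp = 0.03534. At 24 months, true OS = 0.799 + 0.121 = 0.920 against 0.980, a gap of 0.060. At 36 months, 0.714 + 0.142 = 0.856 against 0.970, a gap of 0.114.

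Smallest gap (r = 0.20, d = 0.15, s = 0.50): hr = 0.00372, hd = 0.00271, hp = 0.01155. At 24 months, 0.857 + 0.072 = 0.929 against 0.937, a gap of 0.008. At 36 months, 0.793 + 0.097 = 0.890 against 0.907, a gap of 0.017.

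| r | Gap at 2 years | Gap at 3 years |
|---|---|---|
| 0.20 | 0.008-0.027 | 0.017-0.053 |
| 0.40 | 0.018-0.060 | 0.036-0.114 |

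**Step 5. Which horizons the data can reach.** Section 9.1.3 puts 115-150 of up to 650 patients in the last 9 months (April-December 2019). Assume abstraction in mid-May 2020 (Section 6 says Q2 2020) and even accrual over the earlier 60 months, whose potential follow-up is then 13.5-73.5 months. The share with at least t months is (1 - w)(73.5 - t)/60, with w = 115/650 = 0.177 or 150/650 = 0.231. This gives 63-68% at 24 months, 48-51% at 36 and 17-19% at 60. The 5-year gap in the same model is 4-23 points, but few patients could contribute at that horizon.

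**The case against.** The best reply is that the plan already answers the question. Section 9.7 is the only place that says how overall survival will be programmed, and a specific endpoint rule is normally read over a general description of follow-up. The fields it needs are in 9.3.6, 9.4 sends the physician through the whole record, and part 3 extends outcomes to the latest entry. A programmer working from 9.7 and 9.3.6 would compute ordinary overall survival. Figure 1, to which 9.1 and 9.2 relate, and the DCF might confirm this.

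Most of this stands. Ordinary overall survival is the likelier reading, and on it there is no bias. What remains is that three sections state a different stopping rule, one with explicit first-event wording, and no readable text says that 9.7 prevails.

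The stakes are also low. Overall survival is not among the objectives in Section 8. Section 9.1.2 speaks only of "exploratory models to examine possible factors associated with disease recurrence and disease-free interval, if the sample size is sufficient". Section 9.7 calls the Cox models exploratory, and Section 9.5 plans no formal hypothesis testing. That supports a low grading; it does not remove the conflict.

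A reader might infer that the plan leaves overall survival undefined, or that the survival results will be biased. The documents support neither: 9.7 defines the endpoint, and bias arises only if the window overrides it. Nor should the 4-23 points at 5 years be taken as the expected bias, since they rest on assumed hazards at a horizon few patients could reach.

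**Conclusion.** The text contradicts itself on when observation ends for overall survival. The finding is minor and bears on an exploratory output. Under 9.7 as written the bias is zero. Under the 9.2 window as written, deaths after recurrence are lost and survival is overstated, by an amount the documents cannot supply. The illustrative 1-6 points at 2 years and 2-11 at 3 years depend on constant hazards, no loss to follow-up, and assumed rates of recurrence, death without recurrence and survival after recurrence.

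Time to recurrence fits the window and is unaffected. It would be too much to conclude that every Section 8 objective is therefore untouched: Section 9.1 places referrals and treatment in the same period, and the plan does not say whether those after recurrence count. The conclusion is limited to the readable text; Figure 1 or the DCF could resolve the matter.

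**What to change.** In the Abstract, 9.1 and 9.2, state the end of observation by endpoint. For time to recurrence: recurrence, death or last record entry, whichever comes first. For overall survival: death or last record entry, regardless of recurrence, as 9.7 already has it. State in the same places whether the referral and treatment summaries stop at recurrence. Instruct abstractors to record date of death and date of last encounter for every high-risk patient in parts 2 and 3, recurred or not. Check that Figure 1 and the DCF agree.

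The cost is wording in three places, one abstractor instruction and the check. The date fields exist (9.3.6), and part 3 already returns to the records of earlier high-risk patients (9.1.3). The downside is brief extra chart review for patients who have recurred; the documents give no time per chart.
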